6.2 Use of specimens

The blood and tumor samples collected in this study will be used for FC-9 studies as described in [Section 6.4](#) and for analyses to be conducted in the future related to the purposes of the FC-9 study but not currently described in the protocol. Additionally, the specimens procured may be used for future studies involving gene and proteins conferring susceptibility to cancer or other diseases. Results of the correlative science studies, including raw sequencing data, will not be reported directly to the patient or the physician and will not have any bearing on patient treatment.

The results of the study will be communicated through publication, in peer reviewed scientific literature and/or through presentations at scientific meetings. However, anonymized or de-identified research data (as deemed appropriate by the NSABP), including genome sequencing data, may be submitted to public research databases for data sharing with scientific researchers outside of the NSABP.

6.3 Required tumor and blood sample submission procedures

6.3.1 *Archived primary tumor tissue*

Submission of archived primary tumor block prepared from the diagnostic biopsy or other surgery is a study requirement. If the tumor block is not available, refer to FC-9 Pathology and Correlative Science Instructions for details on alternative submission.

Note: After confirmation by DSSM, patients whose diagnostic sample was previously submitted for participation in NSABP MPR-1 will have met this study requirement. Provide the MPR-1 Patient ID number to DSSM for confirmation of MPR-1 tumor sample submission.

6.3.2 *Study blood samples*

Blood samples will be collected and submitted at 5 time points for each patient:

- Pre-treatment (*prior* to beginning radiation therapy),
- Cycle 1, Day 15
- Cycle 2, Day 1;
- Cycle 4, Day 1, and
- Cycle 6, Day 1.

6.3.3 *Fresh tissue collection*

Required tumor samples will be collected at 2 time points for each patient:

- At pre-treatment prior to radiation; and
- After Cycle 2 (8 weeks).

6.4 Correlative Science Studies

The following correlative science studies are planned to determine the effect of the combination of radiation and dual immune checkpoint blockade with durvalumab plus tremelimumab on immune response in blood and in tumor tissues.

6.4.1 *Immune monitoring of peripheral blood*

- Blood lymphocytes may be analyzed for immune cell gene expression and quantitative changes of lymphocyte subpopulation and immune-related cells prior to radiation and while receiving study therapy.
- Peripheral blood mononuclear cells (PBMC) may be assessed by fluorescence-activated cell sorting (FACS) or with gene expression for changes in cell subsets including, but not limited to, naive and memory CD8⁺ and CD4⁺ T cells, MDSCs, NK, and B cells. The PBMCs may be used to screen for immune response and for functional assays such as an assessment of antibody dependent cell mediated cytotoxicity (ADCC).

6.4.2 *Analysis of circulating tumor DNA and circulating tumor cells*

Peripheral blood mononuclear cells (PBMCs) may also be archived to isolate circulating tumor cells (CTCs) and/or cell free DNA (cfDNA). The cfDNA may be used to profile circulating tumor DNA for mutations, amplifications, gene fusions or other genetic

abnormalities arising during the course of disease or in response to therapy. Analyzing detected cfDNA and CTCs in PBMC may provide further understanding of patient response and explain resistance or sensitivity to therapy.

6.4.3 ***Analysis of tumor infiltrating immune cell populations***

It is expected that immunogenic cell death of cancer cells induced by radiation of an index lesion enhance antitumor immune response. Tumor tissues from unirradiated tumor sites will be procured at baseline prior to radiation and after cycle 2 for further analysis of immune response in tumor. The extent of intratumoral CD8⁺ T and other immune cell infiltrates in tumor tissues may be analyzed and the immunoscore may be determined as reported previously ([Tumeh 2014](#), [Galon 2006](#), [Pages 2005](#), [Llosa 2015](#)). We will use the most appropriate technology at that time.

The tumor/immune microenvironment may be assessed by IHC staining of multiple immune markers utilizing the PerkinElmer's opal-7 color staining system and their Vectra® quantitative pathology imaging systems with the inForm® Advanced Image Analysis system. Multiplex staining of up to 6 different markers enables the identification of helper B cells (CD20), T cells (CD4), cytotoxic T cells (CD8), memory T cells (CD45RO) and regulatory T-cells (FOXP3) in a single section of tissue. Other markers such as PD-L1, PD-1 can also be multiplexed with these immune markers. This allows for not only the quantification of specific types of immune cells but also localizes these cells with respect to the tumor and with respect to each other, an important consideration for assessment of the immune environment.

6.4.4 ***Analysis of gene expression involved in immune checkpoint pathways in tumor tissues***

It is known that multiple immune checkpoint pathways are involved in antitumor immune response. Expression of genes involved in immune checkpoint pathways including PD-L1/2, LAG-3, OX40, GITR, TIM-3, CD137, IDO, markers for MDSCs, and markers associated with immunogenic cell death ([Bezu 2015](#)) may be analyzed by IHC in tumor tissue biopsied at pre-treatment prior to radiation and after cycle 2 (8 weeks) ([Tumeh 2014](#), [Llosa 2015](#)). RNA-Seq and/or the nCounter Vantage™ RNA: Protein Immune Cell profiling panel from NanoString which interrogates the expression of 770 genes and 30 proteins may be used to assess the expression of both the tumor and immune microenvironment.

6.4.5 ***Analysis of the frequency of mutation-associated neoantigens in tumor tissues***

It has been shown that the frequency of mutation-associated neoantigens in tumor tissues correlates with clinical response to immune checkpoint inhibitors in melanoma, lung cancers and MSI-high colorectal cancer ([Le 2015](#), [Alexandrov 2013](#), [Snyder 2014](#), [Rizvi 2015](#)). The frequency of mutation-associated neoantigens in tumor tissues may be analyzed for any significant correlation with clinical response to the study treatment ([Le 2015](#), [Vogelstein 2013](#), [Alexandrov 2013](#), [Snyder 2014](#), [Yadav 2014](#), [Rizvi 2015](#)).

6.4.6 ***Proteomic analysis of signaling pathways***

Protein lysates generated from archived tissue may be used to interrogate signaling pathways using microarrays or related technologies depending on the state of the art at the time these experiments are undertaken. High throughput assays (such as Reverse Phase Protein Microarrays-RPPA for example) allow simultaneous evaluation of the activation status of multiple signaling pathways, by probing for protein phosphorylation, expression levels and other related parameters. Analyzing such changes may provide further understanding of patient response and explain resistance or sensitivity to therapy.

7.0 TREATMENT REGIMEN

Study therapy (Cycle 1/Day1) should begin following three doses of 9 Gy hypofractionated SBRT to a single index lesion on Day – 2, Day –1, and Day 0 *prior* to Cycle 1.

The lesion selected for radiation should be a lesion that can be safely radiated with focal irradiation (SBRT) for which radiation at the limited, palliative doses contemplated would be considered medically appropriate and in accord with acceptable radiation oncology practice. For SBRT guidance, see [Appendix B](#).

7.1 Study therapy

Note: See [Section 9.0](#) for specific study drug information and preparation instructions. Study therapy must be administered in the order outlined in [Table 4](#). See [Table 7](#) for study therapy dose level management.

Table 4. Study therapy (tremelimumab and durvalumab)

Drug	Dose	Administration	Dosing Interval	Planned Duration
Cycles 1–4				
Tremelimumab ^{a,c,d}	75 mg	IV infusion (See footnotes a and c for administration instructions)	1 dose every 4 weeks on Day 1 of cycles 1, 2, 3 and 4 (1 cycle = 4 weeks)	4 cycles
Durvalumab ^{b,c,d}	1500 mg	IV infusion (See footnotes b and c for administration instructions)	1 dose every 4 weeks on Day 1 of cycles 1, 2, 3 and 4 (1 cycle = 4 weeks)	4 cycles
Cycles 5-24				
Durvalumab ^{b,c,d}	1500mg	IV infusion (See footnotes b and c for administration instructions)	1 dose every 4 weeks on Day 1 of cycles 5 through 24 (1 cycle = 4 weeks)	20 cycles

Table 4 continued on next page.

Table 4. Study therapy (tremelimumab and durvalumab) (continued)

a Tremelimumab will be administered as a controlled IV infusion using a low protein binding 0.2 or 0.22 μm in-line filter via infusion pump into peripheral or central venous access. See Section 9.1.
 
– The entire contents of the IV bag should be administered over 60 minutes (+/- 5 minutes) at room temperature (approximately 25°C).– In the event of a \leq Grade 2 infusion reaction, the infusion rate may be decreased or interrupted until resolution of the event and re-initiated at 50% of the initial infusion rate. Subsequent infusions may be administered at 50% of the initial infusion rate.– The standard infusion time is one hour, however if there are interruptions during infusion, the total allowed time from infusion start to completion of infusion should not exceed 8 hours at room temperature, (otherwise requires new infusion preparation).– Following completion of the tremelimumab infusion, flush the IV line with a volume of IV solution equal the volume contained in the tubing or complete the infusion according to institutional policy to assure the full dose is administered. 
Note: A one hour observation period is required between the first dose of tremelimumab and durvalumab and after the first dose of durvalumab. See Table 2. For subsequent doses a 30 minute observation period is recommended between tremelimumab and durvalumab and after durvalumab. See Table 2.


b Durvalumab will be administered as a controlled IV infusion using a low protein binding 0.2 or 0.22 μm in-line filter via infusion pump into peripheral or central venous access. See Section 9.2.
 
– On Day 1 of Cycles 1, 2, 3 and 4, durvalumab will be administered approximately 1 hour after the completion of the tremelimumab IV infusion. Durvalumab (Day 1 of Cycles 5 through and including 24) will be administered as monotherapy.– The entire contents of the IV bag should be administered over 60 minutes (+/- 5 minutes) at room temperature (approximately 25°C).– In the event of a \leq Grade 2 infusion reaction, the infusion rate may be decreased or interrupted until resolution of the event and re-initiated at 50% of the initial infusion rate. Subsequent infusions may be administered at 50% of the initial infusion rate.– The standard infusion time is one hour, however if there are interruptions during infusion, the total allowed time from infusion start to completion of infusion should not exceed 8 hours at room temperature, with maximum total time at room temperature not exceeding 8 hours (otherwise requires new infusion preparation).– Following completion of the durvalumab infusion, flush the IV line with a volume of IV solution equal the volume contained in the tubing or complete the infusion according to institutional policy to assure the full dose is administered.

c Vital Signs will be measured within an hour prior to start of tremelimumab and durvalumab administrations, at 30 minutes during the infusion (\pm 5 minutes), at the end of infusion (+ 5 minutes), and at 30 minutes (\pm 5 minutes) and 60 minutes (\pm 5 minutes) post-infusion. If the infusion takes longer than 60 minutes, then blood pressure and pulse measurements should follow the time increments as outlined at the end of the infusion or more frequently if clinically indicated. For subsequent doses of study therapy, a 30 minute observation period and vital sign check is required unless a patient experiences an infusion-related reaction and requires additional monitoring.


d Allergic reactions to durvalumab and tremelimumab are possible. See Sections 8.5.1 and 8.5.2.
 
– A 1-hour observation period is required following the first infusion of both study drugs.– Acetaminophen and/or an antihistamine (e.g., diphenhydramine) or equivalent medications per institutional standard may be administered at the discretion of the investigator.– The infusion rate of study drug may be decreased by 50% or interrupted as described above– Appropriate drugs and medical equipment to treat acute anaphylactic reactions must be immediately available, and study personnel must be trained to recognize and treat anaphylaxis.

7.2 Supportive therapy

7.2.1 Growth factor support

Use of growth factor support (e.g., G-CSF, GM-CSF) is prohibited.

7.2.2 Erythropoietin

The use of erythropoiesis-stimulating agents is prohibited.

7.2.3 Other supportive care

Patients should receive supportive care for other treatment-related symptoms at the investigator's discretion.

7.2.4 Targeted therapy

While on study, administration of targeted therapy for malignancy is prohibited.

7.3 Contraindications and precautions

- Study therapy, durvalumab and tremelimumab is contraindicated in patients who are pregnant or lactating. See [Section 10.5](#) and [Appendix C](#).
- Immunosuppressive doses of steroids or other immunosuppressive medications through 90 days post last dose of study therapy. See [4.2.10](#). Note however, use of immunosuppressive medications for the management of study therapy-related AEs (see [Section 8.5](#)) or in patients with contrast allergies is acceptable. In addition, use of inhaled and intranasal corticosteroids is permitted.
- Drugs with laxative properties and herbal or natural remedies for constipation should be avoided through 90 days post last dose during the study because of the potential for exacerbation of diarrhea.
- Live attenuated vaccinations during the study or up to 180 days following the last dose of investigational product.
- Patients should not donate blood while participating in this study or for at least 180 days following the last infusion of study therapy.

7.4 Participation in other clinical trials

If a patient on the FC-9 trial is considering participation in another clinical trial (including supportive therapy trials), contact the DSSM (see [Information Resources](#).)

8.0 TREATMENT MANAGEMENT

8.1 General instructions

- The NCI CTCAE v4.0 must be used to grade the severity of AEs.
- All treatment decision must be based on the AE requiring the greatest modification.
- Drug doses that have been reduced may not be re-escalated.
- All hematologic, gastrointestinal, and genitourinary toxicities must be < Grade 2 prior to initiating Dose 1 of study therapy. Patients unable to receive Dose 1 will be considered screen failures.

8.2 Treatment management for durvalumab and tremelimumab

The study treatment schedule should be maintained. If necessary, the timing of a treatment may be adjusted to 3 days earlier or 3 days later than the scheduled date of treatment. All doses administered or missed must be recorded.

8.2.1 *Treatment decisions when therapy must be held*

- In the event systemic steroid therapy is initiated for toxicity management, study therapy must be held. The steroid taper should be completed within 28 days. Study therapy may then be resumed after completion of the steroid taper on Day 1 of the next scheduled cycle.
- Note: Should the steroid taper require a slower rate for completion (i.e., > 28 days), further study therapy doses must be discontinued.
- See [Table 7](#) for treatment management.

8.2.2 *Treatment decisions when therapy must be discontinued*

Treatment must be discontinued if:

- If either durvalumab or tremelimumab must be held for > 28 days of continuous delay for other than steroid taper (e.g., toxicity).
- Consent is withdrawn or patient is lost to follow-up. If consent is withdrawn, the patient will not receive any further investigational product or further study observation.
- An adverse event occurs that, in the opinion of the investigator or sponsor, contradicts further dosing.
- The patient becomes pregnant or intends to conceive a child while actively on study.
- Grade 3 or greater infusion reaction occurs.
- Bullous rash.
- Diagnosis of Guillain-Barre and/or Myasthenia Gravis.
- Initiation of alternate cancer therapy including another investigational agent.
- If tumor progression occurs during study therapy, durvalumab must be discontinued. See [Section 11.0](#).

See [Table 7](#) for additional treatment management requirements. Patients who prematurely discontinue study therapy should complete assessments on [Table 2](#).

8.3 Dose modifications for durvalumab and tremelimumab

The instructions for management of toxicities during durvalumab and tremelimumab are outlined in [Table 7](#). Dosing of study therapy will be done in tandem:

- When study therapy doses are to be maintained, **both** durvalumab and tremelimumab doses will be maintained on the same dose level.

- When a dose reduction is indicated, **both** durvalumab and tremelimumab will be reduced to the same dose level (e.g., Dose level 1).
- When discontinuation of study therapy is indicated, durvalumab and tremelimumab will be discontinued at the same time.

Table 5. Dose levels for durvalumab

Durvalumab	Dose Level 0 Starting Dose	Dose Level –1	Dose Level –2
		1500 mg	750 mg

Table 6. Dose levels for tremelimumab

Tremelimumab	Dose Level 0 Starting Dose	Dose Level –1	Dose Level –2
		75 mg	40 mg

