Platelet count decreased (See Section 8.5.11.)	2	Hold until \leq Grade 1 or baseline, then resume and: Maintain dose or \downarrow one dose level.	Hold until \leq Grade 1 or baseline, then resume and: Maintain dose
	3	Hold until \leq Grade 1 or baseline, then resume and: \downarrow one dose level.	Hold until \leq Grade 1 or baseline, then resume and: Maintain dose
	4	Discontinue study therapy	
	Musculoskeletal and connective tissue disorders		
Myositis/Polymyositis (See section 8.5.13)	1	No dose modifications.	
	2	Hold study therapy dose until resolution to Grade ≤ 1 . Discontinue study therapy if it does not resolve to Grade ≤ 1 within 28 days or if there are signs of respiratory insufficiency.	
	3	Hold study therapy dose until resolution to Grade ≤ 1 . Discontinue study therapy if Grade 3 imAE does not resolve to Grade ≤ 1 within 28 days or if there are signs of respiratory insufficiency.	
	4	Discontinue study therapy	

Table 7 continued on next page.

Table 7. Treatment management for study therapy (continued)

CTCAE v4.0 Adverse Event	CTCAE v4.0 Grade	Action to be Taken with Study Therapy	
		Tremelimumab	Durvalumab
Nervous system disorders			
Neurotoxicity (to include but not be limited to limbic encephalitis and autonomic neuropathy, excluding Myasthenia Gravis and Guillain-Barre) (See Sections 8.5.1 and 8.5.9.)	1	Hold study therapy during neurotoxicity work-up. If diagnosis of Myasthenia Gravis or Guillain-Barre is confirmed, discontinue study therapy. Otherwise, maintain study dose level.	
	2,3	Hold study therapy during neurotoxicity work-up. Once elevations have resolved to \leq Grade 1, and if 
 no systemic steroid therapy has been initiated, then resume: \downarrow 1 dose level. systemic steroid therapy has been initiated –after completion of the steroid taper: resume \downarrow 1 dose level or discontinue If steroid taper completion is $>$ 28 days: discontinue further study therapy. 	
	4	Discontinue study therapy	
Peripheral neuromotor syndrome (such as Guillain-Barre and myasthenia gravis) (See Sections 8.5.1 and 8.5.10.)	1	No dose modifications.	
	2	Hold study therapy dose until resolution to Grade \leq 1. Permanently discontinue study therapy if it does not resolve to Grade \leq 1 within 28 days or if there are signs of respiratory insufficiency or autonomic instability.	

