- Patients unable to tolerate steroids may be candidates for treatment with plasmapheresis or IVIG. Such decisions are best made in consultation with a neurologist, taking into account the unique needs of each patient.
- If Myasthenia Gravis-like neurotoxicity present, consider starting acetylcholine esterase (AChE) inhibitor therapy in addition to steroids. Such therapy, if successful, can also serve to reinforce the diagnosis.

GUILLAIN-BARRE:

- It is important to consider here that the use of steroids as the primary treatment of Guillain-Barre is not typically considered effective.
- Patients requiring treatment should be started with IVIG and followed by plasmapheresis if not responsive to IVIG.

- *Grade 3:*

- Hold study therapy dose until resolution to Grade ≤ 1 .
- Discontinue study therapy if Grade 3 imAE does not resolve to \leq Grade 1 in 28 days.
- Recommend hospitalization.
- Obtain Neurology consult.
- Report event to DSSM.

- *Grade 4:*

- Discontinue study therapy.
- Report event to DSSM.

8.5.11 *Hematologic effect*

Tremelimumab can suppress bone marrow function with myelosuppression as the dose-limiting toxicity. Monitor complete blood cell counts including platelet counts.

- Patients must not begin a new cycle of treatment unless the absolute neutrophil count (ANC) is ≥ 1500 cells/mm³ and platelet count is $\geq 75,000$ /mm³. Follow study therapy management and dose modifications as instructed in [Table 6](#) and [Table 7](#).

Patients with previous history of bleeding and/or who are taking anticoagulant medication may have a higher risk of subsequent bleeding; special attention to monitoring these patients in the context of possible bleeding is warranted ([Durvalumab IB 2018](#)).

8.5.12 *Myocarditis*

The prompt diagnosis of immune-mediated myocarditis is important, particularly in patients with baseline cardiopulmonary disease and reduced cardiac function. Monitor patients for signs and symptoms of myocarditis (new onset or worsening chest pain, arrhythmia, shortness of breath, peripheral edema). As some symptoms can overlap with lung toxicities, simultaneously evaluate for and rule out pulmonary toxicity as well as other causes (e.g., pulmonary embolism, congestive heart failure, malignant pericardial effusion). A Cardiology consultation should be obtained early, with prompt assessment of whether and when to complete a cardiac biopsy, including any other diagnostic procedures.

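### Section 8.3 reduces both drugs together without exception, but the platelet rows of Table 7 reduce tremelimumab alone; the wording of 8.3 needs a minor correction

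*Combined protocol and SAP*

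**What the plan says.** Section 8.3 first sends the reader to a table: "The instructions for management of toxicities during durvalumab and tremelimumab are outlined in" Table 7. It then sets a general principle, "Dosing of study therapy will be done in tandem", with three bullets. Both drugs are maintained on the same level; when a reduction is indicated, both "durvalumab and tremelimumab will be reduced to the same dose level"; and both are discontinued at the same time. None of the bullets carries an exception.

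Table 7 (section 8.4) gives one shared action for both drugs in every row except platelet count decreased. In that entry:

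- **Grade 2:** after the hold, tremelimumab is maintained or lowered one level; durvalumab is maintained.
- **Grade 3:** after the hold, tremelimumab is lowered one level; for durvalumab the cell reads "then resume and: Maintain dose".
- **Grade 4:** both drugs stop.

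The platelet entry cites section 8.5.11, which says "Tremelimumab can suppress bone marrow function with myelosuppression as the dose-limiting toxicity". That section continues "Follow study therapy management and dose modifications as instructed in" Tables 6 and 7. Table 6 holds the tremelimumab dose levels. Section 7.1 also names Table 7 "for study therapy dose level management". No sentence says whether 8.3 or Table 7 governs when they differ.

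**The concern.** One event leads to two different durvalumab doses, depending on which text the site follows. A Grade 3 platelet fall is an event for which a reduction is indicated, because Table 7 lowers tremelimumab. The reduce bullet of 8.3 then takes durvalumab down as well, while the durvalumab cell of the same Table 7 row keeps it where it is.

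At stake is durvalumab exposure in an affected patient. Section 8.1 does not allow a reduced dose to be raised again, and the protocol has no clause for undoing a reduction made in error. Whichever text a site follows, it departs from the other.

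The maintain bullet has the same gap. After a platelet split the drugs sit on different levels, so they cannot both be maintained on the same one.

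**Working it through.** **Inputs.** Starting doses are durvalumab 1500 mg and tremelimumab 75 mg (Table 4). Tables 5 and 6 are broken in the text available, so the first reduced doses come from the dose calculations in section 9, which cite those tables: durvalumab 750 mg (9.2, Preparation) and tremelimumab 40 mg (9.1.4). The protocol's own volumes reproduce:

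- durvalumab: 1500 / 50 = 30.0 mL and 750 / 50 = 15.0 mL
- tremelimumab: 40 / 20 = 2.0 mL

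Taking 750 mg and 40 mg as Level -1 is an assumption, but these are the only reduced doses that section 9 calculates. The Level -2 entries cannot be read.

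**When the conflict can arise.** Tremelimumab is given on Day 1 of Cycles 1 to 4. After an event in Cycle 1, 2 or 3, the tremelimumab doses still due are 4 - 1 = 3, 4 - 2 = 2 or 4 - 3 = 1. After an event in Cycle 4 the next dose is durvalumab alone, so no tremelimumab reduction remains to trigger the tandem rule. The patient must also recover in time to resume, since 8.2.2 discontinues treatment after a continuous hold of more than 28 days.

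**Next doses after a first Grade 3 platelet event**

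| Text followed | Tremelimumab | Durvalumab |
|---|---|---|
| Table 7 | 40 mg | 1500 mg |
| 8.3 bullet, literally | 40 mg | 750 mg |

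Gap per durvalumab dose: 1500 - 750 = 750 mg, and 750 / 1500 = 50%.

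**Cumulative durvalumab through Cycle 4, if every dose is given.** Under Table 7 it is 4 × 1500 = 6,000 mg. Under the literal 8.3 bullet, for an event after the dose of Cycle k, it is k × 1500 + (4 - k) × 750:

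| k | Total | Share of 6,000 mg | Shortfall |
|---|---|---|---|
| 1 | 1,500 + 2,250 = 3,750 mg | 62.5% | 2,250 mg |
| 2 | 3,000 + 1,500 = 4,500 mg | 75% | 1,500 mg |
| 3 | 4,500 + 750 = 5,250 mg | 87.5% | 750 mg |

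Each later durvalumab dose adds 750 mg to the gap. In the extreme case of all 24 cycles, the total is k × 1500 + (24 - k) × 750, that is 18,750, 19,500 or 20,250 mg against 24 × 1500 = 36,000 mg. The shortfall is then 48%, 46% or 44%.

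**Frequency.** The documents give no Grade 3 platelet rate for this combination at these doses. The nearest figure is in section 2.4: one Grade 3/4 autoimmune thrombocytopenia among 45 patients with colorectal cancer on tremelimumab alone, at a different dose and schedule. If 1/45 applied to 21 patients, 21 × 1/45 gives about 0.5 events. The exact 95% limits for the rate correspond to roughly 0.01 to 2.5 events. That count includes Grade 4 and late events, where no conflict exists.

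**Effect on the design.** The decision rule in 14.2 counts responses (stop at 0 of 12; reject at 2 or fewer of 21). No input to it depends on the dose-modification wording.

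**The case against.** The strongest reply is that the documents already point to the right answer. Section 8.3 sets no trigger of its own: a site learns that a reduction is indicated only by reading the Table 7 row, and that row tells it to maintain durvalumab. Sections 7.1 and 8.5.11 also lead to Table 7, 8.5.11 cites the tremelimumab level table and not the durvalumab one, and the general guidance in 8.4 speaks of holding the drug suspected of causing the toxicity. A specific row would normally override a general rule. All of this stands. It means that a site could halve durvalumab, not that it would. It does not remove the mismatch, because the tandem bullets follow the pointer to Table 7 and read as the instruction for carrying a reduction out, with no stated precedence.

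A reader might go further and infer any of the following, which the documents do not support:

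- **That durvalumab is halved whenever the rule applies.** This holds only for a first reduction from the starting level. The effect in a patient already reduced is unknown, because Level -2 is unreadable.
- **That a mistaken cut is locked in.** Section 8.1 can be read as covering only reductions that the protocol directs. Investigators treating a patient must join the weekly call, and a medical review team meets monthly (14.3), so such a case would probably be noticed.
- **That the efficacy result or patient safety is compromised.** Nothing in the documents shows that either dose is unsafe, and few patients, possibly none, would be affected.

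**Conclusion.** The inconsistency is real and lies in the current text, but it is minor. It covers Grade 3 platelet events, and Grade 2 events where the investigator elects to lower tremelimumab. It is confined to Cycles 1 to 3, with tremelimumab still due and the patient resuming within the 28-day limit. For a first such event the two texts differ by 750 mg per durvalumab dose. The cumulative figures are what-if values that assume every dose is given, and the 24-cycle totals are an extreme. The frequency figure rests on borrowing a monotherapy rate and serves only to show that the event is probably rare. The split row is the intended instruction, so the defect is in 8.3 and Table 7 should stand.

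**What to change.** Leave the lead sentence and the discontinuation bullet of 8.3 as they are. Add to the maintain and reduce bullets:

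> *except for platelet count decreased, where each drug is modified separately as given in Table 7; after such a split, each drug is maintained at, or reduced one level from, its own current dose level.*

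The exception belongs in those two bullets and not in the lead sentence, because there it would also loosen the rule that both drugs stop together. That rule must still apply to platelet events, at Grade 4 or when the hold limit is exceeded.

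The second half of the clause is needed for later events. If a patient on tremelimumab 40 mg and durvalumab 1500 mg then has Grade 2 diarrhea, Table 7 calls for one level down. Each drug would step down from where it is, and 8.3 would no longer ask for a common level that the patient has already left.

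The cost is one clause in two bullets, at the next amendment or as a clarification to sites. Sample size, analysis and timeline do not change.
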